8. STUDY POPULATION SUMMARIES

8.1. Enrollment

The total number and percentage of participants for each Analysis Set defined in Section 6 will be summarized by treatment group, also by country and study site/Investigator.

8.2. Subject Disposition

All participants who provide informed consent will be accounted for in this study. The number and percentages of screen failure participants will be presented by overall among the Enrolled Analysis Set. The number and percentages of participants who received at least one dose, completed, are still ongoing and withdrew, including reasons for withdrawal, will be presented overall and by randomized treatment group.

Note that the disposition listing will capture the reason for withdrawal including any subject who discontinues from the study due to COVID-19 related AE, or COVID-19 related.

8.3. Demographic and Baseline Characteristics

Demographics and other baseline characteristics data including age, age group ($<65, \ge 65$), race, ethnicity, sex at birth, weight, height at screening, body mass index, childbearing potential (female only), region, wash out of ET medications prior to Baseline, randomization stratification factors, baseline TETRAS-ADL (items 1-12), TETRAS-PS (items 1-9) and CGI-S will be summarized by treatment group for Safety, ITT, and PK analysis sets. Categorical variables will be summarized by frequency and percentage of participants. The denominators for calculating the percentages will be the number of participants in each analysis set. Continuous variables will be summarized using descriptive statistics including the number of participants, mean, median, standard deviation (SD), minimum and maximum.

8.4. Medical/Surgical History

Surgical and medical history are defined as those medical conditions/ diseases which started prior to or on the date first study dose.

The surgical and medical history data will be summarized based on the Safety Analysis Set and ITT Analysis Set.

8.5. Prior and Concomitant Medications

Medications will be coded to the anatomical therapeutic class (ATC) level 4 and preferred drug name using the WHODrug Global-B3, March 2024, and will be classified as follows:

- **Prior medications** are defined as any medications which started prior to the first dose of study intervention.
- Concomitant medications are defined as any medications which started prior to, on or after the first dose of study intervention up to the last dose of study intervention and continued during the study intervention.
- **Post medications** are defined as any medications which started after the last dose of study intervention.

See Appendix 1: Date Imputation Rules for handling of partial dates for medications.

Medications will be summarized by ATC level 4 and preferred drug name.

Summaries will include all prior medications under ITT and Safety Analysis Set, as well as concomitant medications under the Safety Analysis Set. Additionally, prior and concomitant ET medications will be summarized and listed.

8.6. Protocol Deviations

Protocol deviations as classified in the CTMS (type of deviation and severity) will be summarized using the ITT as well as Safety Analysis Set. All protocol deviations will also be provided in a listing.

Changes to study conduct due to COVID-19 restrictions will be reported as protocol deviations. These deviations will be summarized separately by the classification type in CTMS and included in a listing.

Any IMP dispensing errors will be reported as protocol deviations. For outputs summarized under ITT Analysis Set, participants will be analyzed according to the randomized treatment arm. For outputs summarized under the Safety Analysis Set, actual treatment arm will be mapped according to the planned arm based on randomization schedule, to handle potential drug dispensation error(s) when unblinding, the most frequent dispensed dose (10, 20 or 30 mg) on or after Week 4 will be used, in case the drug dispensation error(s) occurred prior to Week 4, the last dispensed kit upon early discontinuation will be used, for participant who early discontinued on or prior to Day 7 on a 5 mg blister card, 10mg will be assigned as the actual treatment arm.

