4. STUDY DESIGN

4.1. Overall Design

This is a 12-week, double-blind, placebo-controlled, randomized, parallel-group, multicenter study of the safety and efficacy of JZP385 in the treatment of adult participants with moderate to severe ET.

The total duration of the study for each participant will be approximately 19 weeks. During the Screening Period, which will occur over a period of up to 35 days (an additional 28 days are permitted for participants who require washout of primidone), all participants will be evaluated for eligibility and will washout any prohibited medications. Participants may be allowed to rescreen once if the rescreening is approved by the medical monitor.

Participants eligible for the study will be randomized in a 1:1:1:1 ratio to receive once daily doses of 10, 20, or 30 mg JZP385 or placebo during a 12-week Double-blind Treatment Period. Randomization will be stratified by the TETRAS composite outcome score (\leq 17 or > 17) and the use of concomitant antitremor medication (Yes or No), as assessed at the Baseline Visit. JZP385 will be administered orally (PO) once daily in the morning on an empty stomach for 12 weeks. Dosing will be titrated as follows:

- Participants randomized to the 10 mg/day dose will initially receive 5 mg/day from Day 1 through Day 7, and 10 mg/day starting on Day 8.
- Participants randomized to the 20 mg/day dose will initially receive 5 mg/day from Day 1 through Day 7, 10 mg/day from Day 8 through Day 14, and 20 mg/day starting on Day 15.
- Participants randomized to the 30 mg/day dose will initially receive 5 mg/day from Day 1 through Day 7, 10 mg/day from Day 8 through Day 14, 20 mg/day from Day 15 through Day 21, and 30 mg/day starting on Day 22.

Once participants reach their assigned fixed dose, they will continue on that dose for the remainder of the planned 12-week treatment period. No dose adjustments will be allowed. Participants who cannot tolerate their assigned fixed dose of JZP385 will be withdrawn from the study.

Assessments of efficacy, safety, and PK will be conducted as indicated in Section 8.2, Section 8.3, and Section 8.5, respectively, and as described in the Schedule of Activities (SoA) (Section 1.3)

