6.1. Study Intervention(s)/Treatment(s) Administered

The study interventions planned for use in this study are described in Table 4 below.

Protocol JZP385-201-04 Amendment 04

Table 4: Study Treatment/Intervention

Treatment Arm	Intervention/ Treatment Name ^a	Formulation	Unit Dose Strength(s) ^b	Dosage Level(s)	Route of Administration	Use	Sourcing	Package	Labeling	Storage Conditions
1	Placebo	Capsule	Placebo	3 x placebo QD	Oral	Placebo comparator	Provided centrally by the sponsor	Placebo capsules will be provided in blister cards; and labeled as required per country requirement.	Double- blind	Store at 2 to 8°C
2	JZP385 (DR2)	Capsule	Baseline Visit: 5 mg JZP385 Weeks 2-12: 10 mg JZP385	1 x 5 mg QD + 2 x placebo QD 1 x 10 mg QD + 2 x placebo QD	Oral	Experimental	Provided centrally by the sponsor	JZP385 capsules will be provided in blister cards; and labeled as required per country requirement.	Double- blind	Store at 2 to 8°C
3	JZP385 (DR2)	Capsule	Baseline Visit: 5 mg JZP385 Week 2: 10 mg JZP385 Weeks 3-12: 20 mg JZP385	1 x 5 mg QD + 2 x placebo QD 1 x 10 mg QD + 2 x placebo QD 2 x 10 mg QD + 1 x placebo QD	Oral	Experimental	Provided centrally by the sponsor	JZP385 capsules will be provided in blister cards; and labeled as required per country requirement.	Double- blind	Store at 2 to 8°C
4	JZP385 (DR2)	Capsule	Baseline Visit: 5 mg JZP385 Week 2: 10 mg JZP385 Week 3: 20 mg JZP385 Weeks 4-12: 30 mg JZP385	1 x 5 mg QD + 2 x placebo QD 1 x 10 mg QD + 2 x placebo QD 2 x 10 mg QD + 1 x placebo QD 3 x 10 mg QD	Oral	Experimental	Provided centrally by the sponsor	JZP385 capsules will be provided in blister cards; and labeled as required per country requirement.	Double- blind	Store at 2 to 8°C

Abbreviations: mg = milligram; QD = once daily.

^a The JZP385 DR2 formulation is delayed release formulation 2 ie, capsules containing a combination of IR and DR pellets; details of the formulation can be found in the JZP385 IB.

^b The dose strength of JZP385 is based on the active moiety in the drug product.

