5. STUDY DESIGN

5.1. Summary of Study Design

This is a 12-week, double-blind, placebo-controlled, randomized, parallel-group, multicenter study of the safety and efficacy of JZP385 in the treatment of adult participants with moderate to severe ET.

[figure not shown]
The total duration of the study for each participant will be approximately 19 weeks. During the Screening Period, which will occur over a period of up to 35 days (an additional 28 days are permitted for participants who require washout of primidone), all participants will be evaluated for eligibility and will washout any prohibited medications. Participants eligible for the study will be randomized in a 1:1:1:1 ratio to receive once daily doses of 10, 20, or 30 mg JZP385 or placebo during a 12-week Double-blind Treatment Period. Randomization will be stratified by the TETRAS composite outcome score (≤ 17 or > 17) and the use of concomitant antitremor medication (Yes or No), as assessed at the Baseline Visit. JZP385 will be administered orally (PO) once daily in the morning on an empty stomach for 12 weeks. Dosing will be titrated as follows:

- Participants randomized to the 10 mg/day dose will initially receive 5 mg/day from Day 1 through Day 7, and 10 mg/day starting on Day 8.
- Participants randomized to the 20 mg/day dose will initially receive 5 mg/day from Day 1 through Day 7, 10 mg/day from Day 8 through Day 14, and 20 mg/day starting on Day 15.
- Participants randomized to the 30 mg/day dose will initially receive 5 mg/day from Day 1 through Day 7, 10 mg/day from Day 8 through Day 14, 20 mg/day from Day 15 through Day 21, and 30 mg/day starting on Day 22.

Once participants reach their assigned fixed dose, they will continue on that dose for the remainder of the planned 12-week treatment period. No dose adjustments will be allowed. Participants who cannot tolerate their assigned fixed dose of JZP385 will be withdrawn from the study.

The schema of study is shown in Figure 1.

Figure 1 Study Schema

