6. ANALYSIS SETS

For purposes of analysis, the following populations are defined:

Table 4Analysis Sets

Analysis Set	Description		
Enrolled	The Enrolled Analysis Set will include all participants who provide informed consent for this study.		
	This set will be used to summarize participants' screening, and inclusion/exclusion from each analysis set as well as reasons for exclusion. Summaries will be presented overall and by the randomization group for those randomized.		
Intent-to-treat (ITT)	The ITT Analysis Set will include all participants who are randomized regardless of taking the study intervention (JZP385 or placebo). This set will be used for standard, baseline characteristics and demographic summaries, as well to be used for efficacy analyses, and participants should be summarized according to the randomized treatment arm.		
Safety	The Safety Analysis Set will include all participants who are randomized and receive at least 1 dose of study intervention (JZP385 or placebo). This set will be used for standard, baseline characteristics and demographic summaries, as well to be used for safety analyses, and participants should be summarized according to actual received treatment arm.		
PK	The PK Analysis Set will include all participants who are randomized and receive at least 1 dose of JZP385 and have at least 1 post-dose evaluable PK concentration. All PK analyses and summaries will be based on the PK Analysis Set.		

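### Does the Day 7 rule in SAP 8.6 move correctly dosed 20 and 30 mg participants into the 10 mg safety column?

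*SAP*

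**What the plan says.** SAP 6 groups the Safety Analysis Set by treatment received: "participants should be summarized according to actual received treatment arm". SAP 8.6 says how that arm is derived. Its paragraph opens with "Any IMP dispensing errors will be reported as protocol deviations". A single long sentence then does the mapping, in four parts:

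1. Default and purpose: "actual treatment arm will be mapped according to the planned arm based on randomization schedule, to handle potential drug dispensation error(s) when unblinding".
2. First exception: "the most frequent dispensed dose (10, 20 or 30 mg) on or after Week 4 will be used".
3. Second exception: where the error happened before Week 4, the kit most recently given out before the participant stopped decides the arm.
4. Third exception, for a participant "who early discontinued on or prior to Day 7 on a 5 mg blister card, 10mg will be assigned as the actual treatment arm".

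The titration schedule supplies the other half of the picture. SAP 5.1 states "Participants randomized to the 20 mg/day dose will initially receive 5 mg/day from Day 1 through Day 7", Protocol 4.1 states "Participants randomized to the 30 mg/day dose will initially receive 5 mg/day from Day 1 through Day 7", and the 10 mg arm also starts at 5 mg for the first seven days. Protocol Table 4 gives the same first kit, "1 x 5 mg QD + 2 x placebo QD", in each JZP385 arm.

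**The concern.** The second exception carries its own error condition and the third does not. Taken alone, the third has two tests: the participant stopped by Day 7, and was on a 5 mg card. Because that card is the correct first kit in every JZP385 arm, it neither reveals an error nor points to 10 mg. A programmer who coded the clause as a free-standing rule would move every 20 or 30 mg participant who stops in the first week into the 10 mg column.

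Safety and tolerability at each fixed dose is a secondary objective, and SAP 10 uses the Safety Analysis Set for all safety outputs unless otherwise specified. Exposure, TEAEs leading to withdrawal, and TEAEs by time of first onset (which has a Week 1 category) would all be affected. First-week stops would vanish from the two higher doses and collect in the lowest, which could suggest a false inverse dose pattern.

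**Working it through.** **Step 1. What the purpose phrase governs.** Mapping everyone to the planned arm does nothing to handle a dispensing error, so the phrase about errors makes sense only as the introduction to the exceptions that follow it. The paragraph's opening sentence has the same subject.

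**Step 2. Whether the exceptions can be general rules.** The first exception also lacks an error condition of its own. It offers only 10, 20 or 30 mg as results. As a general rule it would give no arm to a placebo participant, and none to anyone who stopped before Week 4. It works only as an exception to the planned-arm default. Not repeating the condition is therefore how the sentence is drafted, and is weak evidence that the third clause stands alone.

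**Step 3. What the third exception is for.** The second exception relies on the last kit. Under the Schedule of Activities kits are given out at Baseline and at Weeks 1, 4 and 8, and the Week 1 visit falls on Day 7 (-1, +2). A participant who stops by Day 7 will usually hold only the Baseline kit. If that is a 5 mg card, the last-kit rule returns 5 mg, which is not an arm. The third exception closes this gap. Example: a placebo participant given a 5 mg card in error who stops on Day 5 has received JZP385, and needs some JZP385 column.

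**Step 4. Participants moved under each reading.**

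Inputs: SAP 5.3 plans 80 evaluable per group with 20% dropout, and 80 / (1 - 0.20) = 100, which matches its 100 randomized per group. Assume that all 100 are treated, that there are no dispensing errors, and that k participants in each JZP385 arm stop by Day 7 on the correct card. The documents give no value for k, and it may be 0.

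- Exceptions limited to errors: nobody moves. Columns are 100 / 100 / 100, with early stops k/100 in each.
- Free-standing rule: 10 mg column = 100 + 2k, 20 and 30 mg columns = 100 - k each. Early stops are 3k/(100 + 2k) under 10 mg and 0/(100 - k) under 20 and 30 mg.

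| k (assumed) | Errors only, each arm | Free-standing, 10 mg | Free-standing, 20 and 30 mg |
|---|---|---|---|
| 0 | 0/100 | 0/100 | 0/100 |
| 1 | 1/100 (1.0%) | 3/102 (2.9%) | 0/99 |
| 3 | 3/100 (3.0%) | 9/106 (8.5%) | 0/97 |
| 5 | 5/100 (5.0%) | 15/110 (13.6%) | 0/95 |

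The last two columns arise only if the code overrides the default stated in the same sentence.

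**Step 5. What cannot be affected.** SAP 8.2 reports disposition, with reasons for withdrawal, by randomized group. SAP 9 presents efficacy by randomized group. Protocol 9.4.5 makes safety descriptive, without formal tests.

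**The case for a change.** The best case for acting is that the text leaves the scope unstated and the repair is cheap. The clause next to it repeats the error condition, SAP 6 and SAP 7.6 do not settle the matter, and one sentence would remove the doubt. A missing condition also matters more here than in the first exception: applied to a correctly dosed JZP385 participant still being supplied after Week 4, the first exception simply returns the planned arm, while the Day 7 clause does not. Early stops are plausible too, since Protocol 4.2 reports that adverse events in the earlier essential tremor study came mainly in the first week.

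Much of this is accurate. The wording is loose, and the columns would shift as shown if the clause were coded alone. But that coding has to set aside the default, the purpose phrase and the error-limited rule that the clause completes. The evidence on early stops is thin: the earlier study started at 8 mg/day (Protocol 4.3) rather than 5 mg, its first-week remark concerns reported events rather than stopping, and Protocol 2.3.1 says most events did not lead to discontinuation.

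One narrow case survives even on the errors-only reading. A 20 or 30 mg participant handed another JZP385 participant's 5 mg kit, who also stops by Day 7, would be counted under 10 mg although the Week 1 regimen was right. That needs two uncommon events in one person. The documents give no rate for either, and each occurrence moves one participant between columns.

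**Conclusion.** The concern does not call for a change. The Day 7 clause is a poorly punctuated sub-case of a rule for dispensing errors, and the sentence around it shows its scope. An analyst who applies the planned-arm default first, and the exceptions only where an error is recorded, moves no correctly dosed participant, and the by-dose safety tables stay as they should be. An added sentence would put the evident scope in writing but alter no result, apart from the rare mis-supplied 20 or 30 mg participant who also stops by Day 7.

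This rests on reading the purpose phrase as governing all three exceptions, which is the only reading that leaves placebo participants and correctly dosed early stoppers with a usable arm. The shifts shown for a free-standing rule depend on an assumed k and do not predict what this trial's tables will show.

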9. EFFICACY

Unless otherwise described, efficacy data will be primarily presented by randomized treatment groups using ITT, and treatment comparison will be between the randomized treatment groups.

9.1. Primary Efficacy Estimand and Analysis

9.1.1. Primary Estimand

The attributes of the primary estimand are listed in Section 4.2.1.

The primary estimand is a composite outcome of the sum of modified items 1 to 11 of the TETRAS-ADL and modified items 6 and 7 of the TETRAS-PS. The scoring of each of the items 1 to 11 of the TETRAS-ADL subscale will be modified from 5 response options to 4 response options by using the following rules:

- A score of 0 or 1 will be modified to a score of 0
- A score of 2 will be modified to a score of 1
- A score of 3 will be modified to a score of 2
- A score of 4 will be modified to a score of 3
- A missing score will remain missing

The scoring of each of the items 6 and 7 of the TETRAS-PS will be modified from 9 options to 4 response options by using the following rules:

- A score of 0, 0.5, or 1 will be modified to a score of 0
- A score of 1.5 or 2 will be modified to a score of 1
- A score of 2.5 or 3 will be modified to a score of 2
- A score of 3.5 or 4 will be modified to a score of 3
- A missing score will remain missing

There are a total of 14 items that contribute to the TETRAS composite outcome score (11 items from the TETRAS-ADL with a total possible score of 33, TETRAS-PS item 6 with a total possible score of 6 as this item includes assessments for both hands, and TETRAS-PS item 7 with a total possible score of 3). Therefore, the total range of the TETRAS composite outcome score that will be used for the primary analysis is 0 to 42.

9.1.2. Primary Analyses

For the main analysis of the primary efficacy endpoint, a MMRM will be used to include the change in the TETRAS composite outcome score from Baseline to Weeks 4, 8, and 12.

$$dTCOM_{ij} = \alpha_i + \beta_1 * baseTCOM_i + \beta_2 * week_j + \beta_3 * treatment_i + \beta_4 * treatment_i * week_j + \beta_5 * baseTCOM_i * week_i + \beta_6 * stratum_i + \varepsilon_{ij}$$

The model will include treatment group ($treatment_i$), baseline TETRAS composite outcome score ($baseTCOM_i$), week (as a discrete factor, $week_j$), treatment group by week interaction ($treatment_k * week_j$), week by baseline interaction ($week_j * baseTCOM_i$), and randomization

stratum ($stratum_i$) as fixed effects, and week repeated within each participant as a repeated effect (α_i). For the purposes of this model, "week" refers to the treatment visit, as determined using the windows specified in Section 7.2.3. An unstructured variance-covariance matrix will be used to model the correlation among repeated measurements. If the model fails to converge on the Newton-Raphson Algorithm, the alternative Fisher scoring algorithm should be explored before considering other variance-covariance structures. Kenward-Roger's degrees of freedom will be used.

Least squares mean and standard error for Week 12 will be provided for each treatment group. The difference between the LS means of JZP385 and placebo for Week 12, along with the SE of the difference, 95% CI and associated p-value corresponding to testing the hypothesis of no difference between the treatment groups will also be provided.

The assumption of normality will be examined by obtaining a histogram and a QQ-plot on studentized residuals. Based on these plots, if there exists evidence to suggest the departure from the normality assumption, a non-parametric MMRM with the covariate and response variables replaced by their ranks will be used for the primary analysis.

The following is an example of SAS code for linear mixed model analysis:

PROC MIXED;

CLASS PATIENT TRT WEEK STRATUM;

MODEL CHG = BASELINE TRT WEEK STRATUM TRT*WEEK BASELINE*WEEK /

RESIDUAL OUTP=RESIDUAL DDFM=KR;

REPEATED WEEK/TYPE=UN SUB=PATIENT;

LSMEANS TRT*WEEK / CL DIFF ALPHA=0.05;

RUN;

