	SV1	SV2 ^b	Baseline Visit	W1	W2, W3	W4	W5, W6, W7	W8	W9, W10, W11	W12	E/D Visit	EoS Visit / Safety FU ^c	Comments
Days (Window)	-35ª	to -2	-1	7 (-1, +2)	14 (-1, +2); 21±3		35±3; 42±3; 49±3	56± 3	63±3; 70±3; 77±3	84± 3		98 ^d ±3	
Clinic Visit	X	X	X	Xe		Xe		Xe		X	Xe	Xe	
Phone Contact					X ^f		X ^f		X ^f				
Activity													
Urinalysis	X		X	X		X		X		X	X		Repeat urinalysis at the Baseline Visit only if the visit occurs > 35 days after screening.
Blood sample for genetic testing				X									The sample is optional and should be collected at the same time as the predose PK sample.
Supine and standing blood pressure and pulse	х	X	х	x		Х		Х		Х	х	х	SV1, SV2 (if applicable), and Baseline: Triplicate measurements at 15- to 30-minute intervals. All other visits: 1 measurement postdose.
Temperature and respiratory rate	X	X	X	X		X		X		X	X	X	
12-lead ECG	х		Х	Х		х		Х		х	х	х	At each time point, ECGs will be taken in triplicate at approximately 2-minute intervals. Additional ECGs may be obtained at any time per the investigator's judgment.

	1	Scree to 35	ning days ^a)		Doub		nd Treatmen 12 weeks)	ıt Peri	od			Safety Follow-up Period (2 weeks)	
	SV1	SV2 ^b	Baseline Visit	W1	W2, W3	W4	W5, W6, W7	W8	W9, W10, W11	W12	E/D Visit	EoS Visit / Safety FU ^c	Comments
Days (Window)	-35ª	to -2	-1	7 (-1, +2)	14 (-1, +2); 21±3	28±3	35±3; 42±3; 49±3	56± 3	63±3; 70±3; 77±3	84± 3		98 ^d ±3	
Clinic Visit	X	X	X	Xe		Xe		Xe		X	Xe	Xe	
Phone Contact					X ^f		X ^f		X ^f				
Activity													
C-SSRS Screening/ Baseline Version	X												
C-SSRS Since Last Visit Version		X	X	X		X		X		X	X	X	
Instruction on medication washout	X	X											
TETRAS-ADL Subscale	X	X	x			X		X		X	X		At SV1, perform the TETRAS-ADL subscale only for participants who do not need to washout of medications that impact tremor (eg, primidone); otherwise, this assessment should be performed at SV2.
TETRAS-PS	x	X	X			X		X		X	X		The TETRAS-PS will be conducted as indicated in Table 5.
CGI-S	х	X	х			Х		Х		х	x		At SV1, perform the CGI-S only for participants who do not need to washout of medications that impact tremor (eg, primidone); otherwise, this assessment should be performed at SV2.

	I	Scree to 35	ning days ^a)		Doub		nd Treatmen 12 weeks)	ıt Peri	od			Safety Follow-up Period (2 weeks)	
	SV1	SV2 ^b	Baseline Visit	W1	W2, W3	W4	W5, W6, W7	W8	W9, W10, W11	W12	E/D Visit	EoS Visit / Safety FU ^c	
Days (Window)	-35ª	to -2	-1	7 (-1, +2)	14 (-1, +2); 21±3	28±3	35±3; 42±3; 49±3	56± 3	63±3; 70±3; 77±3	84± 3		98 ^d ±3	

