5.1. Inclusion Criteria

Participants are eligible to be included in the study only if all of the following criteria apply:

Age

1. Participant must be 18 to 80 years of age inclusive, at the time of signing the informed consent.

Type of Participant and Disease Characteristics

- 2. Participants who are diagnosed with ET (including ET plus) according to the MDS Consensus Statement on the Classification of Tremors from the Task Force on Tremor of the International Parkinson's and Movement Disorder Society (Bhatia, 2018) and centrally reviewed by an Eligibility Adjudication Committee (EAC; see Section 10.1.5).
- 3. Participants have moderate to severe disability associated with tremor at both the Screening and Baseline visits, as determined by all of the following:
 - a. Score of \geq 22 on the TETRAS-ADL subscale; and
 - b. *Note*: This criterion has been removed in Amendment 3.
 - c. CGI-S rating of at least moderate for participants' ability to function.

Note: Participants who need washout of a medication(s) that could impact their tremor assessment (eg, medications that produce tremor **or** that treat tremor but are prohibited because of potential PK drug-drug interactions with study intervention [such as primidone]) at Screening Visit 1 must return to the clinic for a second Screening Visit (Screening Visit 2). For these participants, the Screening TETRAS-ADL subscale and CGI-S assessments that will be used to determine eligibility will be performed at Screening Visit 2, after participants have washed out their medication.

Sex and Contraceptive/Barrier Requirements

- 4. Participant is male or female.
 - a. Male participants:

Male participants are eligible to participate if they agree to the following during the study intervention period and for at least 30 days after the last dose of study intervention:

• Refrain from donating sperm.

PLUS, either:

• Be abstinent from heterosexual intercourse as their preferred and usual lifestyle (abstinent on a long-term and persistent basis) and agree to remain abstinent.

OR

- Must agree to use contraception/barrier as detailed below:
 - Agree to use a male condom with female partner use of an additional highly effective contraceptive method with a failure rate of < 1% per year (as described in Appendix 5) when having sexual intercourse with a woman of childbearing potential (WOCBP) who is not currently pregnant.

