9.4.2. Primary Estimand

The primary estimand is a composite outcome score of the sum of modified items 1 to 11 of the TETRAS-ADL and modified items 6 and 7 of the TETRAS-PS. For the primary estimand, the scoring of each of the items 1 to 11 of the TETRAS-ADL subscale as well as items 6 and 7 of the TETRAS-PS will be modified. For TETRAS-ADL, each item will be modified from 5 response items to 4 response items by collapsing options 0 and 1 together and for TETRAS-PS, each item will be modified from 9 response items (due to 0.5 scoring increments) to 4 response items. Each item has a maximum score of 3. As item 6 of the TETRAS-PS includes assessments for both hands, there are a total of 3 items from the TETRAS-PS and 11 items from the TETRAS-ADL that contribute to a 14-item TETRAS composite outcome score. The total range of the TETRAS composite outcome score that will be used for the primary analysis will therefore be 0 to 42.

The attributes of the primary estimand are listed below:

- Treatment: 10, 20, and 30 mg/day JZP385 and placebo.
- Population: Adults with moderate to severe ET.
- Variable: Change from Baseline to Week 12 on the TETRAS composite outcome score.
- Intercurrent Events:
 - Discontinuation of study intervention due to an AE, for lack of efficacy, or any other reason. Participants who experience this type of intercurrent event will be addressed by hypothetical strategy.
 - Any change to concomitant antitremor medication use after the initiation of study intervention (refer to Section 9.4.1.2). Participants who experience this type of intercurrent event will be addressed by treatment policy.
- Summary: Difference in the mean TETRAS composite outcome score from Baseline to Week 12 between each dose of JZP385 and placebo.

For the main estimator analysis, a MMRM will be used to include the difference in the TETRAS composite outcome score from the Baseline Visit to Weeks 4, 8, and 12. The model will include fixed effects for treatment group, week, treatment group by week interaction, baseline TETRAS composite outcome score stratification (≤ 17 or > 17), baseline concomitant antitremor medication stratification (Yes or No), baseline TETRAS composite outcome score by week interaction, baseline TETRAS composite outcome score as a continuous covariate, and week repeated within each participant as a repeated effect. An unstructured variance-covariance matrix will be used to model the correlation among repeated measurements.

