7.2. Baseline and Study Day Definitions

7.2.1. Baseline

In general, the Baseline measurement for a variable is defined as the last non-missing value from the baseline visit measured prior to the first dose of the study intervention. If a participant has repeated measurements from the baseline visit, then the last repeated non-missing value will be used. If there is not a value from the scheduled baseline visit, the last non-missing value from other screening or unscheduled visits measured prior to the first dose of study intervention will be used. If a participant who early discontinued without taking the study intervention, the Baseline visit or the latest Screening Visit will be used.

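### The primary MMRM is valid but leaves unused the Screening TETRAS-ADL, a second pre-randomisation reading; adding it is an optional, near-free gain in precision of uncertain and modest size.

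*SAP*

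**What the plan says.** **Model.** The SAP 9.1.2 code reads "MODEL CHG = BASELINE TRT WEEK STRATUM TRT*WEEK BASELINE*WEEK". Protocol 9.4.2 agrees on the pre-treatment score: it lists the "baseline TETRAS composite outcome score as a continuous covariate", its interaction with week, and the two randomisation strata. Neither document has a Screening term.

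**Role of Screening values.** SAP 7.2.1 uses them only as a fallback: "If there is not a value from the scheduled baseline visit, the last non-missing value from other screening or unscheduled visits" taken before first dose stands in for Baseline. They are neither averaged with Baseline nor used as a covariate.

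**Data available.** Protocol 5.1, criterion 3, states: "Participants have moderate to severe disability associated with tremor at both the Screening and Baseline visits", which includes a TETRAS-ADL score of at least 22. The Schedule of Activities fixes when the Screening reading is taken: "At SV1, perform the TETRAS-ADL subscale only for participants who do not need to washout of medications that impact tremor"; "otherwise, this assessment should be performed at SV2". Rescreening waives only the TETRAS-PS (Protocol 5.4), and Protocol 5 bars eligibility waivers.

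**The concern.** A single Baseline reading carries day-to-day and rater noise, so it measures each participant's starting level imperfectly. A second reading taken before randomisation can sharpen that estimate and reduce the residual variance at Weeks 4, 8 and 12. Because it precedes randomisation, adjusting for it changes neither the estimand nor the hypotheses, and it leaves Type I error control intact.

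What is at stake is precision on the three primary comparisons. The fixed sequence in SAP 7.4 stops at the first failure, so precision on the 30 mg primary test bears on the five tests that follow it.

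**Working it through.** **1. The plan's own figure.** SAP 5.3 gives 80 evaluable participants per arm, a difference of 3.1, a common SD of 6.0 and a 2-sided 0.05 t-test. Noncentrality is 3.1 / (6.0 × √(2/80)) = 3.1 / 0.949 = 3.27 on 158 degrees of freedom. Power is 90.1%, and 80 is the smallest n per arm that reaches 90%. The stated 90% reproduces.

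**2. Coverage of the covariate.** Eleven ADL items at 0 to 3 give 33 points; PS item 6 (both hands) gives 6 and item 7 gives 3, for a total of 42 (SAP 9.1.1). The SAP recoding can be applied to the Screening ADL items as collected. The full Screening composite is less suitable, because rescreened participants may lack a Screening TETRAS-PS.

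**3. Reduction in residual variance.** Let B be Baseline, S Screening and P Week 12. Adding S to a model that already contains B multiplies residual variance by 1 − R², with

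R² = (r_SP − r_BP × r_SB)² / [(1 − r_BP²)(1 − r_SB²)].

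The documents give none of these correlations, so all are assumed. For r_BP = 0.6 and r_SB = 0.8 the denominator is 0.64 × 0.36 = 0.2304:

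| r_SP | Numerator | R² |
|---|---|---|
| 0.60 (Screening as good as Baseline) | 0.12² | 6.3% |
| 0.55 | 0.07² | 2.1% |
| 0.50 | 0.02² | 0.2% |
| 0.48 (= 0.6 × 0.8) | 0 | 0 |

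Over r_BP 0.5 to 0.7 and r_SB 0.75 to 0.85:

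- If S predicts Week 12 exactly as well as B, R² is 2.7 to 13.7%.
- If r_SP is 0.05 lower than r_BP, R² is 0.3 to 7.0%.
- If r_SP is 0.10 lower, R² is about 0 to 2.5%.

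A simulation imposed ADL ≥ 22 at both visits and used an ADL-only Screening score. Over six settings it gave 3.0 to 7.1%. It placed Screening and Baseline symmetrically around a stable true level, so it does not include decay of correlation with time.

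A reasonable range is therefore roughly 0 to 7%.

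**4. Starting power of the planned model.** SAP 5.3 supports the 6.0 with SDs of change from baseline of 5.86 and 5.47 in the phase 2 study. With equal variances σ² at Baseline and Week 12, the variance of change is 2σ²(1 − r) and the Baseline-adjusted residual variance is σ²(1 − r²). The residual SD is then 6.0 × √((1 + r)/2):

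| r | Residual SD | Planned power | With R² = 5% | Gain (points) |
|---|---|---|---|---|
| 0.5 | 5.20 | 96.3% | 97.0% | 0.7 |
| 0.6 | 5.37 | 95.3% | 96.1% | 0.9 |
| 0.7 | 5.53 | 94.1% | 95.1% | 1.0 |

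Gains are taken from unrounded values.

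**5. Confidence interval.** At r = 0.6 the 95% half-width is 1.975 × 5.37 × √(2/80) = 1.68 points. With R² = 5% it is 1.68 × √0.95 = 1.63.

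**The case against.** The strongest reply is that nothing is wrong. The model already adjusts for the continuous Baseline composite, its week interaction and the strata, and the power statement reproduces. One pre-treatment score is a legitimate choice. This stands: the point concerns efficiency only.

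The benefit is also assumed. The Screening score is earlier than Baseline and covers only the ADL part, so it probably predicts Week 12 less well, and the gain shrinks quickly as it does. This stands too, and it is why the range starts at zero.

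Three stronger readings are tempting, and the documents do not support them.

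- A reader might infer a variance reduction above 10%. On the grid above, that needs Screening to predict Week 12 about as well as Baseline does.
- A reader might start from 90.1% and count 91.5% (5% less variance) or 92.8% (10% less) as the gain. That treats 6.0 as the residual SD after Baseline adjustment, whereas SAP 5.3 supports it with SDs of change.
- A reader might argue that Baseline regresses to the mean because entry depended on it, while Screening does not. Criterion 3 applies the same threshold at both visits, so both readings are selected.

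The last objection is that the change is more than one line of code. SAP 9.1.3 to 9.1.5 reuse the primary model, the imputation models should match it, and `PROC MIXED` drops records with a missing covariate, which would conflict with the ITT set. Where Screening has replaced a missing Baseline value, the two scores would also overlap. These are real but small, and the fix below handles the matching and missing-value points.

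**Conclusion.** The point holds as an optional improvement. The planned primary analysis is valid, and nothing in the documents suggests that it is biased or underpowered on its own assumptions.

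The facts are firm: the model omits a Screening score that every participant randomised per protocol has. The size is not. It depends on visit-to-visit correlations that the documents do not report, on equal variances at Baseline and Week 12, and on reading 6.0 as an SD of change. On those assumptions a 5% variance reduction is worth about 1 percentage point of power or less, and the trial would notice it chiefly as an interval about 2.5% narrower (√0.95 = 0.975). If Screening carries nothing beyond Baseline, the gain is zero and only a few degrees of freedom are spent.

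**What to change.** Before unblinding:

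1. Add the Screening sum of modified TETRAS-ADL items 1 to 11 (SV1, or SV2 for washout participants) and its interaction with week to the MMRM in SAP 9.1.2. Declare the change in SAP 7.6.
2. Add the same covariate to the imputation models in SAP 9.1.3.
3. Apply the ADL item-imputation rule in SAP 7.2.5 to the Screening items. Fill any wholly missing Screening score with the overall mean, ignoring treatment, so that no ITT participant is dropped.

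The cost is about three degrees of freedom (one for the main effect, two for the interaction with three weeks) and minor programming. No new data are needed. Once the blind is broken, the adjustment could serve only as a post hoc analysis.
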